7.3.2. Additional considerations

7.3.2.1. All planned VE Analyses and corresponding risk periods

This section describes all VE analyses (planned in protocol and additional analyses).

For each endpoint, the time at risk will be calculated separately. The time at risk will be counted in days, and expressed as person years at risk (days/365.25). In order to avoid mathematical problems because of time equals zero when an event occurred the same day that the time at risk started, the first day counts as 1 thus the duration is calculated as (date of event or censoring – date of start follow up +1). Time at risk will end at the date of next visit minus 1 to avoid including post safety and efficacy data that may have occurred on the same day.

For endpoints evaluating all episodes where time at risk does not end when the episode meets the case definition, 14 days following the episode will be subtracted from the time at risk (day of episode + 14). If an episode is detected during a period of time not counting for the time at risk it will not be included in the analysis however a table will be presented showing the number of such episodes not included in the analysis.

Table 3 Risk periods for clinical malaria & incident infection for the exposed set

Risk Period (months)	Start of risk period (at subject level)	End of risk period (at subject level)*	Group comparisons	Clinical malaria	Incident Infection
M20 analys	es				
[0-14]	Day of first vaccination of RTS,S or	Date of Month 14 visit – 1 or drop out date	Fx017-20 vs control Fx012-14 vs control	First or only- and all episodes First or only-	First or only episode First or only
	control vaccine	from study conclusion, whichever occurs first	R012-20 +R012-14 vs control Fx012-14 Vs R012-20	and all episodes First or only- and all episodes First or only-	episode First or only episode First or only
[0-20]	Day of first vaccination of	Date of Month 20 visit – 1 or	+R012-14 Fx017-20 vs control	and all episodes All episodes	episode First or only episode
	RTS,S or control	drop out date from study	Fx012-14 vs control	All episodes	First or only episode
	vaccine	conclusion, whichever	R012-20 vs control	All episodes	First or only episode
		occurs first	R012-14 vs control	All episodes	First or only episode
			Fx012-14 Vs R012-20	All episodes	First or only episode
			Fx012-14 Vs R012-14	All episodes	First or only episode
M32 analys		Data af Marath	F-047 00	All:	LAIA

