[6.5 months post dose 3]	14 days post dose 3 of RTS,S (day of	Fx017-14: Date of Month 14-1 or drop out date from study	Fx017-20 vs Fx012-14	First or only- and all episodes	First or only episode
[M7.5-M14] [2.5-9]	dose 3 vaccination + 14)	conclusion, whichever occurs first All other groups: Date of Month 9 or drop out date from study conclusion, whichever occurs first	Fx017-20 vs R012-20 +R012- 14	First or only- and all episodes	First or only episode

204889 (Malaria-094) Statistical Analysis Plan

Risk Period (months)	Start of risk period (at subject level)	Stop (maximum)*	Group comparisons	Clinical Malaria	Incident infection
Analyses 12 i	months post dose	e 3: fractional dose vers	us full dose		
[1 year post dose 3] [M7.5-M19]	14 days post dose 3 of RTS,S (day of dose 3	R012-20: Date of Month 14-1 or drop out date from study conclusion, whichever	Fx017-20 vs Fx012-14	First or only- and all episodes	First or only episode
[M2.5-M14]	vaccination + 14)	occurs first All other groups: Date of the visit of fourth dose -1 or drop out date from study conclusion, whichever occurs first	Fx017-20 vs R012-20 +R012- 14	First or only- and all episodes	First or only episode

^{*} if visit date and last contact date are both missing then subjects will be censored at month [x] times 30.5 days post dose 3.

Clinical Malaria

The rules for calculating the risk periods are the same as for the exposed set.

Incident infection

Only subjects with a confirmed negative blood slide at the beginning of the follow-up period (defined in Table 2 and Table 3) will be included in the analysis. The subjects will be followed-up until being censored (either having a case, having a missing cross-sectional visit or being a drop-out whichever occurs first). For follow-up periods starting from M2.5 and M7.5, only subjects with a confirmed negative blood slide at M2 and M7 will be included in the analysis.

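### Incident-infection windows that close the day before the closing visit drop that visit's survey slide, and the Table 5 end dates differ between schedules

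*SAP*

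**What the plan says.** The general rule in SAP 7.3.2.1 is "Time at risk will end at the date of next visit minus 1", and the reason given is "to avoid including post safety and efficacy data that may have occurred on the same day". Tables 3 and 4 repeat it row by row, for example "Date of Month 14 visit – 1 or drop out date", with a single end date serving both the clinical malaria and the incident infection columns.

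Incident infection (SAP section 4; protocol 4.2) is a positive slide at a cross-sectional survey, or a passively detected case meeting the secondary clinical definition. Surveys are monthly to Month 20. For the windows that open at Month 2½ and Month 7½, "only subjects with a confirmed negative blood slide at M2 and M7 will be included in the analysis". The follow-up rules for incident infection make no exception for the slide taken at the closing visit. In the paragraph on all-episode endpoints the SAP adds: "If an episode is detected during a period of time not counting for the time at risk it will not be included in the analysis".

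The first row of Table 5 (6.5 months post-dose 3) has two different end dates: "Fx017-14: Date of Month 14-1 or drop out date" and "All other groups: Date of Month 9 or drop out date". Table 4 closes the same Month 2½-9 window at the Month 9 visit minus 1. The second row of Table 5 is labelled Month 7.5-19 against Month 2.5-14. It ends R012-20 at Month 14 minus 1 and every other group the day before its fourth-dose visit.

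**The concern.** Visit minus 1 suits clinical malaria, where an episode has its own presentation date and the rule costs one day. An infection found at a survey is dated by the visit, so the same rule removes the one slide that covers the last month of the window. The stated reason does not fit that slide: a positive on a dosing day reflects infection acquired before the dose, and no group is vaccinated at Month 9 or Month 19 (protocol Table 23).

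Two things are at stake. Valid first infections, on slides that are taken and read anyway, drop out of the window they belong to. In Table 5, arms that are compared directly have different numbers of usable slides, which can move the hazard ratio when there is no true difference.

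**Working it through.** **The SAP's own person-time examples.** Subject A, incident infection: 3 × 30.5 = 91.5 (stated 92). Subject A, clinical malaria: 7 × 30.5 = 213.5 (stated 214). Subject B: 10 × 30.5 − 2 × 14 = 277 (stated 277). All reproduce. The SAP's duration formula adds one day to the length but does not move the end date, so it does not bring the closing slide back.

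**Slides per window.** The closing slide is dated V and the last day at risk is V − 1.

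| Window | Slides with closing visit | Counted as written |
|---|---|---|
| [0-14] | 14 | 13 |
| [0-20] | 20 | 19 |
| [2½-9], [7½-14] | 7 | 6 |
| [2½-14], [7½-19] | 12 | 11 |
| [2½-20] | 18 | 17 |
| [M14-M20] | 6 | 5 |

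The Month 9 slide still falls inside [2½-14], and the Month 14 slide inside [0-20] and [2½-20]. The three windows above that reach Month 20 all close at that visit minus 1, and SAP section 10 limits incident infection to Month 20, so the Month 20 slide counts in no incident-infection window.

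**Events lost where arms share the rule.** The documents give no infection incidence; protocol 11.4 says only that it should exceed that of clinical malaria (0.5 per person-year in controls). Assume a constant hazard λ, slide detection only, K monthly slides and S(k) = exp(−λk/12). Share lost = [S(K−1) − S(K)] / [1 − S(K)].

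- K = 7, λ = 0.5: (0.7788 − 0.7470) / 0.2530 = 12.6%. λ = 2: (0.3679 − 0.3114) / 0.6886 = 8.2%.
- K = 6 ([M14-M20]): 15.0% and 10.6%.
- K = 12 ([2½-14]): 6.6% and 2.8%.

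Passive detection in the last month lowers these shares.

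**Table 5, first row, as written.** Fx017-20 has slides M8-M13 (6); comparators have M3-M9 (7). Expected events per 250 children at equal true risk are 250 × [1 − S(6)] against 250 × [1 − S(7)]: at λ = 0.5, 55 against 63; at λ = 1, 98 against 111; at λ = 3, 194 against 207.

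Simulated with true hazard ratio 1 (60,000 per arm, unadjusted Cox, λ = 0.5 to 3):

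- Visits exactly aligned: 0.99-1.01. The extra comparator events occur when no Fx017-20 child is left in the risk set.
- Visits jittered by ±4 days, or with cumulative intervals of 26-35 days: 0.87-0.96 with slides only, and 0.92-0.98 if half of infections present passively.
- Same closing rule in both arms (6 against 6, or 7 against 7): 0.97-1.02, which is 1 within simulation noise.

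A second simulation with visit SD of 3-7 days, λ = 0.5 to 2 and 0-40% passive detection gave 0.86-0.96. The allowed monthly interval is 21-35 days, so some jitter is to be expected.

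**Table 5, second row, as written.** Dose 4 for Fx017-20 is at Month 20, so its window runs to Month 20 minus 1: slides M8-M19 (12), against M3-M13 (11) for comparators, with about one month more follow-up than the label. Table 4 closes [7½-19] at Month 19 minus 1. The simulated null hazard ratio is about 1.01-1.04 with jitter, against Fx017-20.

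**The case against.** The best defence is that visit minus 1 gives consecutive windows that do not overlap, that it treats arms alike wherever they share it, and that the first row of Table 5 is a slip. The general rule covers each endpoint, Table 4 closes the same comparator window at Month 9 minus 1, and the same Table 5 cell names a group, Fx017-14, that does not exist. Read under the general rule, the row has six slides against six and no tilt. This is plausible. It still leaves two contradictory end dates that have to be reconciled before programming, and it does not bring back the closing slide.

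It is also fair that the slide's exclusion is inferred from the end date. The sentence on episodes outside the time at risk sits with the all-episode endpoints, whereas Tables 3 and 4 analyse incident infection as first or only episode. The inference needs only the end date, so it stands.

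A reader might go further and infer that closing slides are never counted, that a child first positive at Month 14 appears nowhere, or that every infection window lacks its last survey. The documents do not support this. Such a child is censored as uninfected in [2½-14] and cannot enter [M14-M20], but can count in [0-20] and [2½-20]. All survey slides feed the prevalence tabulations, subject to the 14-day exclusion around clinical malaria. Passive cases up to the day before the visit count. Table 4's [1-7] row is written to close at the Month 14 visit minus 1, so its Month 7 slide is inside.

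**Conclusion.** The point holds with limits. As written, the closing survey slide falls outside the incident-infection window that the visit closes. Where arms share the rule, this costs about 8-13% of first infections in seven-slide windows, 11-15% in [M14-M20] and 3-7% in [2½-14]. These figures assume a constant hazard of 0.5-2 per year and slide detection only. The loss is of events and precision; it would be wrong to read a directional bias into these windows.

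The risk of bias is confined to Table 5. The first row, programmed literally, gives a null hazard ratio of about 0.86-0.98, a spurious 2-14% incremental efficacy for Fx017-20. That range depends on assumed jitter, hazard and passive detection, falls to nothing with aligned visits, and comes from an unadjusted model, whereas the SAP adjusts for site and monthly control prevalence. The second row tilts slightly the other way.

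The primary clinical-malaria endpoint loses one day and is essentially unaffected. The infection analyses are secondary and descriptive under SAP section 8. The second-row end date does, however, also govern the clinical-malaria comparison of Fx017-20 with full doses over 12 months, which section 8 places second in the testing hierarchy. That effect has not been sized here.

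**What to change.** In SAP 7.3.2.1 and Tables 3-5:

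- Keep visit minus 1 for clinical malaria.
- For incident infection, end the window on the closing survey visit in every arm and count that visit's slide as an event on that date.
- In Table 5, use one closing rule for all arms. The first row ends at Month 14 for Fx017-20 and Month 9 for the others (7 slides each). The second row ends at Month 19 for Fx017-20 and Month 14 for the others (12 slides each), matching the row labels and the months in Table 4.
- Correct the Fx017-14 label, and reconcile the end date of Table 4's [1-7] row with its title.

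The cost is a sentence and some table cells. The slides are collected and read under the existing schedule, so no new data are needed. Consecutive infection windows would then share a boundary visit, whose slide closes one window and sets the negative starting status for the next; one clause should say so.

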1.2.1. Rationale for the study design

A recent CHMI study (MALARIA-071) ***demonstrated superior protection against malaria infection*** associated with the use of a fractional third dose in a 0, 1, 7-month schedule with a vaccine efficacy against infection of 86.7% (95% CI: 66.8; 94.6; p<0.0001) versus 62.5% (95% CI: 29.4; 80.1; p=0.0009) in the standard 0, 1, 2-month schedule. The incremental efficacy of the 0, 1, 7-month schedule over the 0, 1, 2-month schedule was 64.4% (95% CI: -7.9; 88.3; p=0.0741) [Regules, 2016]. The current study intends to establish POC for a fractional dose schedule under conditions of natural exposure. The study will be conducted in children 5-17 months old at first vaccination living in areas of mid to high malaria transmission, in line with the age group recommended by the World Health Organization (WHO) [WHO, 2016]. Infants 6-12 weeks old will not be included in this POC study to avoid interference of co-administration with the standard Expanded Program on Immunization (EPI) vaccines.

Results from this study will be critical in informing future possibilities for the development of vaccine-based strategies which, in combination with other interventions, may contribute to the malaria elimination agenda.

The study proposed herein will include five study groups. One group (R012-20) will receive the standard schedule consisting of RTS,S/AS01_E full dose given at Month 0, Month 1, Month 2 and a fourth dose at Month 20. This corresponds to the schedule that received a positive scientific opinion from EMA. The four other groups will receive alternative schedules as follow:

- Group R012-14-mD will receive RTS,S/AS01_E full dose at Month 0, Month 1, Month 2, an early fourth dose at Month 14 and yearly full doses at Month 26 and Month 38.
- Group Fx012-14-mFxD will receive RTS,S/AS01_E full dose at Month 0 and Month 1, RTS,S/AS01_E fractional dose (1/5th dose) at Month 2 and yearly fractional doses at Month 14, Month 26, Month 38.
- Group Fx017-mFxD will receive RTS,S/AS01_E full dose at Month 0 and Month 1, RTS,S/AS01_E delayed fractional third dose (1/5th dose) at Month 7 and yearly fractional doses at Month 20 and Month 32.
- Control group: will receive three doses of rabies vaccine at Month 0, Month 1 and Month 2.

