Record SAEs related to study participation, or to a concurrent GSK medication/vaccine		●	●	●	●		●	●	●			●	●			●	●		●					
Record SAEs (All, fatal, related to the investigational vaccine) ^p		●	●	●	●		●	●	●			●	●			●	●		●					
Record AEs of specific interest ^l		●	●	●			●	●	●			●	●			●	●		●					
Study Conclusion																								

CONFIDENTIAL

204889 (MALARIA-094)
Protocol Amendment 3 Final

Epoch	Epoch 001												Epoch 002				Epoch 003				Epoch 004			
	Visit 1 ^m Screening	Visit 2	Visit 3	Visit 4	Visit 5 ^a	Visit 6 ^a	Visit 10 ^b	Visit 11 ^b	Visit 12 ^b	Visit 18 ^c	Visit 19 ^c	Visit 24 ^d	Visit 25 ^e	Visit 27 ^c	Visit 28 ^c	Visit 30 ^f	Visit 31 ^f	Visit 33 ^c	Visit 34 ^c	Visit 38				
Type of contact: Clinic visits	D-28 to D-1	D0	M1	M2	M2 + 7d	M3	M7	M7 + 7d	M8	M14	M15	M20	M21	M26	M27	M32	M33	M38	M39	M50				
Timepoints																								
Children age (Months)		5-17 m																						
For the reactogenicity sub-cohort only:										●	●	●												
Blood sampling for assessment of safety (1.0 ml)																								
Record solicited local and general AEs (Days 0-3)								● ^j						● ^j				● ^j						

Note: The double-line border following Month 21 (Visit 25) and Month 33 (Visit 31) indicates the two interim analyses which will be performed on all data collected up to respectively Month 21 and up to Month 33 (i.e. data that are as clean as possible, except clinical malaria fully cleaned up to Month 14). The final analysis will be performed on fully cleaned data collected up to study end (Month 50).

D: Day, M: Month.

● is used to indicate a study procedure that requires documentation in the individual eCRF.

O is used to indicate a study procedure that does not require documentation in the individual eCRF.

- a. Clinic visit 5 (Month 2 + 7 days) and clinic visit 6 (Month 3) are only for groups R012-20, R012-14-mD, Fx012-14-mFxD and Control. The group Fx017-mFxD has a field worker visit at Month 3 for assessment of parasitemia.
- b. Clinic visit 10 (Month 7), clinic visit 11 (Month 7 + 7 days) and clinic visit 12 (Month 8) are only for group Fx017-mFxD. The other groups have field worker visits at Month 7 and Month 8 respectively for assessment of parasitemia.

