11.7.6. Secondary analyses of efficacy

A) Clinical malaria:

Early follow-up time periods (up to Month 14): Vaccine efficacy against first or only episode as well as all episodes of clinical malaria will be assessed both in the ATP and TVC cohorts.

Longer follow-up time periods (longer than Month 14): Vaccine efficacy against all episodes of clinical malaria will be assessed on the TVC. The analysis of vaccine impact will also be performed on the TVC.

Analysis performed at Month 21:

- Incremental efficacy of Fx012-14-mFxD versus (R012-20 + R012-14-mD) over M2.5-M14 (all episodes, ATP).
- Incremental efficacy of Fx012-14-mFxD versus (R012-20 + R012-14-mD) over D0-M14 (first or only and all episode, TVC).
- Vaccine efficacy of Fx012-14-mFxD versus Control group over M2.5-M9 (first or only and all episodes, ATP).
- Vaccine efficacy of Fx017-mFxD versus Control group over M7.5-M14 (first or only and all episodes, ATP).

- Vaccine efficacy of R012-20 + R012-14-mD versus Control group over M2.5-M9 (first or only and all episodes, ATP).
- Vaccine efficacy of Fx012-14-mFxD versus Control group over M2.5-M14 (first or only and all episodes, ATP).
- Vaccine efficacy of Fx017-mFxD versus Control group over M7.5-M19 (first or only and all episodes, ATP).
- Vaccine efficacy of R012-20 + R012-14-mD versus Control group over M2.5-M14 (first or only and all episodes, ATP).
- Incremental efficacy taking into account incidence in controls: Fx017-mFxD/Control group over M7.5-M14 versus Fx012-14-mFxD/Control group over M2.5-M9 (first or only and all episodes, ATP).
- Incremental efficacy taking into account incidence in controls: Fx017-mFxD/Control group over M7.5-M14 versus groups (R012-20 + R012-14-mD)/Control group over M2.5-M9 (first or only and all episodes, ATP).
- Incremental efficacy taking into account incidence in controls: Fx017-mFxD/Control group over M7.5-M19 versus Fx012-14-mFxD/Control group over M2.5-M14 (first or only and all episodes, ATP).
- Incremental efficacy taking into account incidence in controls: Fx017-mFxD/Control group over M7.5-M19 versus groups R012-20 + R012-14-mD/Control group over M2.5-M14 (first or only and all episodes, ATP).
- Vaccine efficacy of R012-20 + R012-14-mD versus Control group over D0-M14 (first or only and all episodes, TVC).
- Vaccine efficacy of Fx012-14-mFxD versus Control group over D0-M14 (first or only and all episodes, TVC).

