7.3.1.6. Secondary analyses of efficacy

A) Clinical malaria:

Analysis performed at Month 20:

- Incremental efficacy of Fx012-14 versus (R012-20 + R012-14) over M2.5-M14 (all episodes, PPS).
- Incremental efficacy of Fx012-14 versus (R012-20 + R012-14) over D0-M14 (first or only and all episode, ES).
- Vaccine efficacy of Fx012-14 versus Control group over M2.5-M9 (first or only and all episodes, PPS).
- Vaccine efficacy of Fx017-20 versus Control group over M7.5-M14 (first or only and all episodes, PPS)
- Vaccine efficacy of R012-20 + R012-14 versus Control group over M2.5-M9 (first or only and all episodes, PPS).
- Vaccine efficacy of Fx012-14 versus Control group over M2.5-M14 (first or only and all episodes, PPS).
- Vaccine efficacy of Fx017-20 versus Control group over M7.5-M19 (all episodes, PPS).
- Vaccine efficacy of R012-20 + R012-14 versus Control group over M2.5-M14 (first or only and all episodes, PPS).

- Incremental efficacy of Fx017-20 over M7.5-M14 versus Fx012-14 over M2.5-M9 (first or only and all episodes, PPS).
- Incremental efficacy of Fx017-20 over M7.5-M14 versus groups R012-20 + R012-14 over M2.5-M9 (first or only and all episodes, PPS).
- Incremental efficacy of Fx017-20 over M7.5-M19 versus Fx012-14 over M2.5-M14 (first or only and all episodes, PPS).
- Incremental efficacy of Fx017-20 over M7.5-M19 versus groups R012-20 + R012-14 over M2.5-M14 (first or only and all episodes, PPS).
- Vaccine efficacy and impact of R012-20 + R012-14 versus Control group over D0-M14 (first or only for efficacy and all episodes for efficacy and impact, ES).
- Vaccine efficacy and impact of Fx012-14 versus Control group over D0-M14 (first or only for efficacy and all episodes for efficacy and impact, ES).
- Vaccine efficacy and impact of Fx017-20 versus Control group over D0-M14 (first or only and all episodes, ES).
- Vaccine efficacy and impact of R012-20 versus Control group over D0-M20 (all episodes, ES).
- Vaccine efficacy and impact of R012-14 versus Control group over D0-M20 (all episodes, ES).
- Vaccine efficacy and impact of Fx012-14 versus Control group over D0-M20 (all episodes, ES).
- Vaccine efficacy and impact of Fx017-20 versus Control group over D0-M20 (all episodes, ES).

Analysis performed at Month 32:

- Vaccine efficacy and impact of R012-20 versus Control group over D0-M26 (all episodes, ES).
- Vaccine efficacy and impact of R012-14 versus Control group over D0-M26 (all episodes, ES).

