Only subjects with a confirmed negative blood slide at the beginning of the follow-up period (defined in Table 3) will be included in the analysis. The subjects will be followed-up until either having a case, or being censored (having a missing cross-sectional visit or being a drop-out whichever occurs first).

Example: the subject A described in the previous example would have been censored at the start of month 4 and contributes (3*30.5) 92 days to the time at risk.

Risk periods for prevalent parasitemia & Gametocytemia

At month 20 there are two types of analysis that will be presented:

- First, the prevalence of parasitemia/gametocytemia will be tabulated for each group (Fx017-20, Fx012-14, R012-20, R012-14 and control) at each cross sectional visit (from M0 until M20).
 - Within gametocytes positive slides the mean male/female ratio will be tabulated by group and time point and by site.
 - Within parasitemia positives the geometric mean with will be tabulated by group and time point and by site.
- Second, an analysis with endpoint all episodes of prevalent infections within risk period [M1-M20] will be performed comparing the groups (Fx017-20, Fx012-14, R012-20, R012-14) with the control. In this analysis subjects with missing visits before the last contact date will only contribute to the time at risk at the time periods

they are not missing. See example below. The subject contributes (3*30.5) + (2*30.5) = 153 days to the time at risk.

• In both analyses described above subjects with clinical malaria (case definition 1 or 2) at start day of detection of parasitemia + subsequent 14 days will be excluded.

At month 32 and month 50 the following analyses will be performed for each group, at each cross sectional visit and by site:

- the prevalence of parasitemia/gametocytemia
- male/female ratio for gametocytes positive slides
- and geometric means for parasitemia positives

Table 4 Risk periods for clinical Malaria & incident infection for the per protocol set: Comparisons with equal calendar times

Risk Period (months)	Start of risk period (at subject level)	End of risk period (at subject level)*	Group comparisons	Clinical Malaria	Incident infection
Analyses 1	2 months post do	se 3:			
• Prima	ary objective: incr	emental efficacy of f	ractional dose versus fu	II dose	
• Seco	ndary objective: v	accine efficacy of al	l groups versus controls	;	

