[2½-14]	14 days post dose 3 of RTS,S or	Date of Month 14 visit – 1 or drop out date from	Primary objective: Fx012-14 vs R012-20 +R012-14	First or only- and all episodes	First or only episode
	control vaccine (day of dose 3	study conclusion, whichever occurs	Fx012-14 vs control	First or only- and all episodes	First or only episode
	vaccination + 14)	first	R012-20 +R012-14 vs control	First or only- and all episodes	First or only episode
-	months post dos	e 2 and 3: groups versus contro	ols		
[2½-9]	14 days post dose 3 of RTS,S or	Date of Month 9 visit – 1 or drop out date from	R012-20+ R012-14 vs Control	First or only- and all episodes	First or only episode
	control vaccine (day of dose 3 vaccination +	study conclusion, whichever occurs first	Fx012-14 vs control	First or only- and all episodes	First or only episode

204889 (Malaria-094) Statistical Analysis Plan

Risk Period (months)	Start of risk period (at subject level)	End of risk period (at subject level)*	Group comparisons	Clinical Malaria	Incident infection
[7½-14]	14 days post dose 3 of RTS,S or control vaccine (day of dose 3 vaccination + 14)	Date of Month 14 visit – 1 or drop out date from study conclusion, whichever occurs first	Fx017-20 vs control	First or only- and all episodes	First or only episode
[1-7]	Day of second vaccination of RTS,S or control vaccine	Date of Month 14 visit – 1 or drop out date from study conclusion, whichever occurs first	Fx017-20 vs control	First or only- and all episodes	First or only episode

Analyses up to 38 months after dose 3:

- incremental of fractional dose versus full dose
- vaccine efficacy of all groups versus controls

[2½-20]	14 days post dose 3 of	Date of Month 20 visit – 1 or drop	Fx012-14 vs control	All episodes	First or only episode
	RTS,S or control vaccine	out date from study conclusion,	R012-14 vs control	All episodes	First or only episode
	(day of dose 3 vaccination +	whichever occurs first	R012-20 vs control	All episodes	First or only episode
	14)		Fx012-14 vs R012-20	All episodes	First or only episode
			Fx012-14 vs R012-14	All episodes	First or only episode
			R012-20 vs R012-14	All episodes	First or only episode
[7½-19]	14 days post dose 3 of RTS,S or control vaccine (day of dose 3 vaccination + 14)	Date of Month 19 visit – 1 or drop out date from study conclusion, whichever occurs first	Fx017-20 vs control	All episodes	First or only episode
[2½-26]	14 days post	Date of Month 26/	R012-14 vs control	All episodes	NA

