[2½-32]	dose 3 of	32/38/50 visit – 1	Fx012-14 vs control	All episodes	
[2½-38] [2½-50]	RTS,S or control vaccine	or drop out date from study	R012-20 vs control	All episodes	
[2/2-50]	(day of dose 3	conclusion,	Fx012-14 vs R012-20	All episodes	
	vaccination +	whichever occurs	Fx012-14 vs R012-14	All episodes	
	14)	first	R012-20 vs R012-14	All episodes	
[7½-26] [7½-32] [7½-38] [7½-50]	14 days post dose 3 of RTS,S or control vaccine (day of dose 3 vaccination + 14)	Date of Month 26/32/38/50 visit – 1 or drop out date from study conclusion, whichever occurs first	Fx017-20 vs control	All episodes	NA

Risk Period (months)	Start of risk period (at subject level)	End of risk period (at subject level)*	Group comparisons	Clinical Malaria	Incident infection
Analyses po	ost booster dose	(post dose 4, 5 and	6):		
[M14-M20]	Day of fourth RTS,S dose or	Date of Month 20 visit – 1 or drop	Fx012-14 vs R012-14	All episodes	First or only episode
	month 14 visit for control	out date from study conclusion,	R012-14 vs control	All episodes	First or only episode
		whichever occurs first	Fx012-14 vs control	All episodes	First or only episode
[M14-M26] [M26-M32]	Day of fourth/fifth/sixth	Date of Month 26/32/38/50 visit –	Fx012-14 vs R012-14	All episodes	NA
[M26-M38]	RTS,S dose or	1 or drop out date	R012-14 vs control	All episodes	
[M38-M50]	month 14/26/38 visit for control	from study conclusion, whichever occurs first	Fx012-14 vs control	All episodes	
[M20-M32]	Day of fourth	Date of Month 32	Fx017-20 vs R012-20	All episodes	NA
	RTS,S dose or month 20 visit	visit – 1 or drop out date from	Fx017-20 vs Control	All episodes	
	for control	study conclusion, whichever occurs first	R012-20 vs Control	All episodes	
[M32-M50]	Day of fifth RTS,S dose or M32 visit for control	Date of Month 50 visit – 1 or drop out date from study conclusion, whichever occurs first	Fx017-20 vs Control	All episodes	NA

^{*} if visit date and last contact date are both missing then subjects will be censored at month [x] times 30.5 days post dose 2/3/4/5/6.

Table 5 Risk periods for clinical Malaria & incident infection for the per protocol set: Comparisons with unequal calendar time

Risk Period (months)	Start of risk period (at subject level)	Stop (maximum)*	Group comparisons	Clinical Malaria	Incident infection
Analyses 6 m	onths post dose	3: fractional dose versu	s full dose		

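### SAP Tables 4 and 5: three risk-period date rules contradict their own labels, most seriously a Control start at Month 2.5 in the six Month 7.5 comparisons with Fx017-20

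*SAP*

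**What the plan says.** SAP 7.3.2.1 sets the subject-level start and end of each risk period.

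- **Table 4, Month 7.5 periods.** The table is titled "Comparisons with equal calendar times". Its six periods [7½-14], [7½-19], [7½-26], [7½-32], [7½-38] and [7½-50] (three printed rows) compare Fx017-20 with Control. All use one start rule: "14 days post dose 3 of RTS,S or control vaccine (day of dose 3 vaccination + 14").
- **Control schedule.** Protocol 1.2.1: "Control group: will receive three doses of rabies vaccine at Month 0, Month 1 and Month 2".
- **Intended start.** SAP 7.3.1.6 lists "Vaccine efficacy of Fx017-20 versus Control group over M7.5-M14 (first or only and all episodes, PPS"), and Protocol 11.7.6 lists "Vaccine efficacy of Fx017-mFxD versus Control group over M7.5-M14 (first or only and all episodes, ATP"). The SAP's incident-infection rule adds: "For follow-up periods starting from M2.5 and M7.5, only subjects with a confirmed negative blood slide at M2 and M7 will be included".
- **Booster rows of the same table.** Control is anchored by visit, for example "Day of fifth RTS,S dose or M32 visit for control".
- **Table 4, row [1-7].** It starts at the second vaccination and ends the day before the Month 14 visit, the same end as the row above it. Tables 6 and 7 list the analysis as M1-M7 and describe it as efficacy of the delayed fractional third dose.
- **Table 5, 12 months post dose 3, labelled M7.5-M19 and M2.5-M14.** Only R012-20 ends by reference to Month 14. Every other group ends the day before its fourth-dose visit, which for Fx017-20 is Month 20. Table 4 ends the same M7.5-M19 period the day before the Month 19 visit.

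**The concern.** These columns are what a programmer turns into code, and nothing elsewhere in the SAP overrides them.

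The Control start matters most. As written, the first-episode Cox model for [7½-14] sets Control in M2.5-M9 against Fx017-20 in M7.5-M14: another calendar period, and children five months younger. Protocol 1.2.2 justifies having a Control group partly because comparing different periods risks seasonal bias. The written rule brings that bias back.

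Row [1-7] as written no longer isolates the time before Fx017-20's third dose. Even with the right end date, a window that closes at the third dose cannot measure that dose's efficacy, so the stated objective does not fit either.

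The Table 5 row defines the window for the one secondary comparison that SAP section 8 places in the hierarchical test, so its end date should be unambiguous.

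**Working it through.** **Convention.** SAP 7.3.2.1 counts 30.5 days per month and both end days. This reproduces its worked examples: 7 × 30.5 = 213.5 (stated 214), 10 × 30.5 − 28 = 277 (stated 277) and 3 × 30.5 = 91.5 (stated 92). With start = dose day + 14 and end = visit − 1, the duration is visit day − (dose day + 14).

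**1. Control start.** Dose 3 is at Month 2 for Control and Month 7 for Fx017-20.

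| Period | Control as written (days) | Fx017-20 (days) | Ratio |
|---|---|---|---|
| [7½-14] | 352 | 199.5 | 1.76 |
| [7½-19] | 504.5 | 352 | 1.43 |
| [7½-26] | 718 | 565.5 | 1.27 |
| [7½-32] | 901 | 748.5 | 1.20 |
| [7½-38] | 1084 | 931.5 | 1.16 |
| [7½-50] | 1450 | 1297.5 | 1.12 |

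Control has 152.5 days (5 months) too many each time. For [7½-14] that is 11.5 against 6.5 months.

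**Effect on estimated efficacy (by assumption).** Let k be the Control rate in M2.5-M7.5 divided by the later rate, taken from 0.5 to 2. True VE comes from the planning rates in Protocol 11.4: 1 − 0.29/0.5 = 42% and 1 − 0.16/0.5 = 68%.

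*All episodes*, with L the correct length in months and the 14-day subtraction ignored: VE_est = 1 − (1 − VE) / [(5k + L)/(5 + L)].

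- L = 6.5, k = 0.5: the divisor is 9/11.5 = 0.783, giving 1 − 0.58/0.783 = 25.9%, or 59.1% for VE 68%.
- L = 6.5, k = 2: the divisor is 16.5/11.5 = 1.435, giving 59.6%, or 77.7%.
- L = 42.5: 38.8% to 47.5%, or 66.2% to 71.0%.

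*First episode, Cox, [7½-14].* Time runs from each child's own start. Control's hazard is k·h for 5 months and then h, with h = 0.5 per person-year. Fx017-20's hazard is (1 − VE)h for 6.5 months. After 6.5 months only Control is at risk, so that time adds nothing to the partial likelihood. With equal arms, the hazard ratio θ solves ∫[f_F(1 − p) − f_C·p]dt = 0, where p = θS_F/(θS_F + S_C), f is the event density and S the survival function.

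| True VE | k = 0.5 | k = 1 | k = 2 |
|---|---|---|---|
| 42% | 4.7% | 42.0% | 67.6% |
| 68% | 47.6% | 68.0% | 82.1% |

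Varying h from 0.25 to 2 per person-year moves the k = 0.5 and k = 2 results to 1.5-5.2% and 67.4-68.8% (VE 42%), and to 46.3-47.8% and 82.0-82.6% (VE 68%).

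*Staggered enrolment.* Assume a yearly cycle with hazard h(1 + 0.5cos), a 3:1 peak-to-trough ratio, over all phases, and even enrolment over W months. For VE 42% the Cox estimate is 17-60% (W = 6), 31-51% (W = 9) and 42% (W = 12). For VE 68% it is 54-78%, 62-73% and 68%.

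**2. Row [1-7].** As written: 13 × 30.5 = 396.5 days. On its label: 6 × 30.5 = 183 days. Seven of the 13 months (54%) follow Fx017-20's third dose.

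**3. Table 5, M7.5-M19.** Fx017-20 as written: 13 × 30.5 − 14 = 382.5 days. On its label: 12 × 30.5 − 14 = 352 days, equal to the nominal M2.5-M14 time of the comparators. From the allowed dose intervals (364-420 days for Fx017-20; 336-392 for Fx012-14 and R012-14), less 14, the ranges are 350-406 against 322-378 days: 28 more.

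No efficacy effect was calculated for incident infection, where the Month 7 slide rule also acts, or for the covariate-adjusted Table 5 model.

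**The case against.** The intended windows are hardly in doubt. Labels, heading, analysis lists and slide rule all point to Month 7.5, Tables 6 and 7 say M1-M7, and Table 4 gives the Month 19 end. A careful programmer might follow the label and treat the cells as copied text. That is fair as to intent, but the date rule is the operative text, and the booster rows show that the SAP states a visit-based Control start when it wants one.

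The reach is limited. SAP section 10 replaced the Control-anchored indirect comparison with the covariate-adjusted direct one in 7.3.1.1, so the Control start enters neither the primary nor the hierarchical test. Section 8 makes the other secondary results descriptive. Fx017-20 against Control from Day 0, over M20-M32 and over M32-M50 is unaffected. All of this stands.

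On Table 5, SAP 7.3.2.4 applies a Schoenfeld residual test to the hierarchical comparison, which implies a Cox model. At nominal dates no comparator child is still at risk in Fx017-20's extra month, so that month adds nothing to a first-episode estimate; visit windows leave only a few days of overlap. It counts only in the all-episodes version. This also stands.

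Finally, the efficacy ranges rest on assumed seasonality, and the single-population model ignores stratification by the two sites. Two equal sites with opposite seasonal phase would give about 42% at a true 42%; sites in phase would not cancel. The ranges show what could happen and do not predict what will.

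**Conclusion.** Wrong as written, and worth correcting before programming. All three rules contradict their labels, and the date arithmetic needs no assumption: five extra months of Control time in each Month 7.5 period, 13 months instead of 6 in row [1-7], and about one extra month for Fx017-20 in Table 5.

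The Control start is the substantive error. It can distort every post-dose-3 efficacy estimate of the delayed fractional schedule against Control, strongly over [7½-14] and weakly over [7½-50]. The size depends on the assumed early-to-late rate ratio of 0.5 to 2 and on near-simultaneous enrolment. It vanishes under a constant rate or even 12-month enrolment. The Table 5 error is small. The primary M2.5-M14 comparison is untouched, because all its groups receive dose 3 at Month 2 and end at Month 14.

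**What to change.** - **Table 4, all six Month 7.5 periods:** start Control at its Month 7 visit date + 14 days. For clinical malaria, state a nominal start for a missed Month 7 visit; the table's footnote covers censoring dates only. Incident infection needs none, because a child without a confirmed negative Month 7 slide is already excluded.
- **Table 4, row [1-7]:** end at the Month 7 visit (Fx017-20's dose 3) − 1. Reword the objective in Tables 6 and 7 as efficacy after two doses, before the third.
- **Table 5, M7.5-M19:** end Fx017-20 at the Month 19 visit − 1, as Table 4 already does.

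With these dates both arms have 199.5 days in [7½-14] and 352 in [7½-19]; row [1-7] has 183 days, and Table 5 has 352 days on each side.

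The cost is SAP wording and a few lines of derivation code. No new data are needed: the parasitemia surveys cover Months 7 and 19 in every group, and for Month 7 Protocol 6.5 says of the groups other than Fx017-20: "The other groups have field worker visits at Month 7 and Month 8 respectively for assessment of parasitemia".
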